- The Timed Up-and-Go (TUG) test will be completed. Four, 90-second trials of walking will then be completed to assess gait under normal and cognitive dual task conditions. Standing postural control will be assessed by measuring postural sway with mobile sensors during 2 repetitions each of 30-second trials of standing—two with eyes open, two with eyes closed, and two while performing the serial subtraction cognitive task.
- Option B: The Timed Up-and-Go (TUG) test will be completed and supervised via a secured Zoom Platform.

Genetic Testing

- Blood samples will be collected for BDNF levels and DNA to assess brain-derived neurotrophic factor (BDNF) Val66Met polymorphism and the presence of apolipoprotein-E (APOE) e4 allele. We will store blood samples for future examination of other potential genetic, epigenetic, metabolic or pro-inflammatory markers.

Aerobic Capacity

- The Incremental Shuttle Walking Test (ISWT) will be performed to determine maximal walking velocity and walk distance. These values will be used to predict VO² peak changes over time as a measure of aerobic capacity. The test will be used to dose the aerobic exercise intensity. Additionally, changes in VO² peak will be assessed for relationship with neuroplasticity and cognitive changes. The participants will be closely monitored (Heart rate, Blood pressure, rate of perceived effort) prior, during and after the test.
- Option B: We will adapt our exercise assessment to a submaximal aerobic capacity assessment using the 1-minute Sit-to-Stand Test (1-MSTST)³³ which can be completed in the participant's home. The 1-MSTST will be performed to determine maximal repetitions completed in one minute without using upper limbs. These values will be used to predict changes in aerobic capacity over time. The test is submaximal and will be used to dose the aerobic exercise intensity. Additionally, changes in aerobic capacity will be assessed for any relationship with neuroplasticity and cognitive changes. The participants will be closely monitored (heart rate, blood pressure, rate of perceived effort, and oxygen saturation) prior to, during and after the test.

9) Procedures Involved*

Study Design

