This is an investigator-initiated open label study in neurologically healthy sedentary adults. Participants will undergo a total of 29 or 31 sessions, including the screening session, three to four pretest (baseline) assessments, 24 aerobic exercise sessions and three to four post-test assessments. For option A, assessments will take place at the Neuromotor Plasticity Lab located at Lois Pope Life Center located at [name] and aerobic exercise visit will take place at either the UMMSM Medical Wellness Center or the UM Coral Gables Wellness Center. For option B, assessments and exercise sessions will take place in the participant home as they are monitored by a trained study member. An illustration of the experimental design is provided below:

Methods:

Subjects will participate in the Option A pending appropriateness based on current University of Miami recommendations and standard operating procedures as it relates to the COVID-19 pandemic. Given the COVID-19 pandemic, it is worth of note that potential participants may remain less enthusiastic about in-person procedures for an undetermined length of time. Thus, even in the event that the study team obtains approval to resume activities as per Option A based on University guidelines, we would like to continue to offer Option B according to participant preference. All testing procedures described for the Option A will be adapted (as feasible) for the Option B. Testing procedures that differ for the Option B are described and noted in the Option B methods.

OPTION A METHODS

TMS Plasticity

Subjects will come in for a total of 2 plasticity visits (pre and post training). We will measure plasticity in the motor cortex of the dominant hand.

Subjects will be set up in a chair with EMG electrodes placed on the first dorsal interosseus (FDI) on the dominant hand to measure motor threshold over in the corresponding (contralateral) motor cortex (M1). The motor threshold serves as the basis for the following TMS-measures over the motor cortex. When administering TMS, the figure of eight coil will be placed tangentially to the scalp with the handle pointing posterior for all stimulations. We will proceed with determining motor threshold and conduct TMS (single pulse TMS and TBS) over the dominant motor cortex. After removing the EMG equipment from the subject, a post TMS safety evaluation will be conducted.

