We will adapt our exercise assessment to a submaximal aerobic capacity assessment using the 1-min sit-to-stand test⁴¹ which can be completed in the participant's home. Participants will be asked to join a zoom meeting where they will be asked to confirm their current geographical location and phone number. Participants will put on the heart rate monitor (Polar) and activity monitor (Actigraph). After this, vitals will be taken after 3-5 minutes of seated rest. Blood pressure, heart rate, and oxygen saturation will be documented by the investigator, and participants will complete a daily exercise questionnaire. The participant will then be asked to stand up and sit down from a sturdy chair for one-minute while being monitored by a trained study member. The number of sit-to-stands performed in 1 minute will be recorded. The participant's heart rate will be monitored continuously throughout the test and heart rate and blood pressure will be taken and documented immediately after the assessment. Heart rate and blood

IRB Study Number: 20180926

pressure will be taken again after 5 minutes of seated rest and will be continued to be monitored until the participant has returned within 20% of their baseline measurement.

Exercise Questionnaires

Questionnaires and surveys will be completed by the participant using a REDCap link sent via a secured email. We are expanding our questionnaire to include a battery of structured surveys used to assess the 7 ‘pillars’ of Brain Health (cognitive function, physical exercise, nutrition, comprehensive health, socialization, sleep, and vital plan [perceived meaning in life]), developed by the Barcelona Brain Health Initiative.⁴²

Adaptation of Our Physical exercise Intervention

We have modified our 2-month, 3x/week in-person exercise intervention to be safely delivered

Scenario 01 Personal Equipment	Scenario 02 No Equipment

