as a home-based exercise program. The study team will setup a zoom call to discuss the plan the exercise delivery modes, which will be individually planned, based on each participant’s available resources and personal situations. For instance, participants whom have access to aerobic exercise equipment at home (treadmill, elliptical, or stationary bike) will be able to use them in the same manner as option A with a remote investigator monitoring and instructing. Individuals who do not have exercise equipment at home will be given a routine of exercises that do not require any equipment, and can be done safely in their homes. The body-weight exercise program was developed by a group of 4 physical therapists (one who is the Principal Investigator of the study) who are part of this study team. Modifications for each exercise will be tailored individually based on participant’s ability levels and safety. Regardless of mode of exercise, the participant will warm up for 5 minutes, have 40 minutes of exercise, and 5 minutes to cool down. Mandatory rest and water breaks will be incorporated into the exercise session every 8 minutes for two minutes each, for a total of 10 minutes of rest breaks during the exercise session. The following figure shows a sample of exercise types for both scenarios.

Each session, participants will join a zoom meeting with a trained study personnel to ensure safety and guide the participant through the exercise session. The participant will be asked to put on the heart rate monitor and provide their geographical location and phone number as per our safety of exercise

IRB Study Number: 20180926

Time	Personal Equipment Group		Time	Body Weight (No Equipment) Group	
Minutes 0:00-4:59	Warm-up 5 Minutes		Minutes 0:00-4:59	Warm-up 5 Minutes	
Minutes 5:00-14:59	Block 1 Steady State Aerobic	Total Time=10 minutes	Minutes 5:00-14:59	Block 1 Body Weight A/B	Total Time=10 minutes
		Work= 8 minutes			Work= 8 minutes
		Rest and Water= 2 minutes			Rest and Water= 2 minutes
Minutes 15:00-24:59	Block 2 Steady State Aerobic	Total Time=10 minutes	Minutes 15:00-24:59	Block 2 Body Weight C/D	Total Time=10 minutes
		Work= 8 minutes			Work= 8 minutes
		Rest and Water= 2 minutes			Rest and Water= 2 minutes
Minutes 25:00-34:59	Block 3 Steady State Aerobic	Total Time=10 minutes	Minutes 25:00-34:59	Block 3 Body Weight E/F	Total Time=10 minutes
		Work= 8 minutes			Work= 8 minutes
		Rest and Water= 2 minutes			Rest and Water= 2 minutes

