Minutes 35:00-44:59	Block 4 Steady State Aerobic	Total Time=10 minutes	Minutes 35:00-44:59	Block 4 Body Weight G/H	Total Time=10 minutes
		Work= 8 minutes			Work= 8 minutes
		Rest and Water= 2 minutes			Rest and Water= 2 minutes
Minutes 45:00-54:59	Block 5 Steady State Aerobic	Total Time=10 minutes	Minutes 45:00-54:59	Block 5 Body Weight I/J	Total Time=10 minutes
		Work= 8 minutes			Work= 8 minutes
		Rest and Water= 2 minutes			Rest and Water= 2 minutes
Minutes 55:00-60:00	Cool-down 5 Minutes		Minutes 55:00-60:00	Cool-down 5 Minutes	

plan. Heart rate, oxygen saturation, and blood pressure will be documented by study personnel after 5 minutes of seated rest. Participants will then complete the daily exercise questionnaire to ensure it is safe to begin exercising. The participant will have continuous heart rate monitoring throughout the intervention sessions using the heart rate monitor (Polar) and activity monitor CentrePoint Software (Actigraph, USA) permitting investigators the ability to monitor patients remotely and in near real-time. Participants heart rate and rate of perceived exertion at will be recorded at frequent intervals. Mandatory rest and water breaks will be implemented to ensure proper hydration.

Exercises will follow a standard format to ensure safety and adherence to study goals (See following table). All participants will complete a guided 5-minute warm-up. The intervention will be structured in five, 10-minute timed blocks consisting of eight minutes of exercise and two minutes of rest. For the body-weight group, participants will be shown two exercises. They will perform exercise "A" for one minute then exercise "B" for one minute. The participant will then repeat A-B sequence three more times for a total of 8 minutes of exercise. The participant will then take a rest and water break for two minutes to complete block one. The participant will complete five blocks using this format, completing a total of 10 unique exercises. The participant will then be guided through a cool down where they will slowly decrease exercise vigor to bring their heart rate down to baseline levels. Following exercise, the participant will be asked to take their blood pressure, heart rate and oxygen saturation and will monitored until the participant has returned within 20% of their baseline measurement.

10) Data and Specimen Banking*

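### In Option B the only aerobic-capacity measure is a one-minute sit-to-stand count; some participants without equipment may also train that movement, and the Aim 2 analysis has no term for exercise scenario.

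*Combined protocol and SAP*

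**What the plan says.** Study Endpoints (section 8, Aerobic Capacity) replaces Option A's shuttle walk with the one-minute sit-to-stand test in Option B: "The 1-MSTST will be performed to determine maximal repetitions completed in one minute without using upper limbs". It continues: "These values will be used to predict changes in aerobic capacity over time". The Option B Exercise Testing text in section 9 confirms what is taken from the test: "The number of sit-to-stands performed in 1 minute will be recorded". No other aerobic-capacity outcome is named for Option B.

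The result feeds Aim 2. Section 8 says that "changes in aerobic capacity will be assessed for any relationship with neuroplasticity and cognitive changes", and the Objectives (section 2) list aerobic capacity among the changes to be associated.

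The Option B intervention text in section 9 splits participants by equipment. Scenario 01 uses a treadmill, elliptical or stationary bike. Scenario 02 uses body-weight exercises, with sit to stand and squat among the six pictured. The menu is illustrative: "The following figure shows a sample of exercise types for both scenarios". On format, each exercise lasts one minute within an A-B pair, and "The participant will then repeat A-B sequence three more times for a total of 8 minutes of exercise". Per session, "The participant will complete five blocks using this format, completing a total of 10 unique exercises".

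Data Analysis (section 11) adjusts for age, sex, race-ethnicity and education. It has no term for study option or exercise scenario.

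**The concern.** The outcome and one possible training exercise are the same movement, with the same bout length. If a participant practises sit to stand for eight weeks, a higher count at the post-test can come from better fitness, stronger legs, or skill at the task. The plan has nothing that separates these. It is an open-label pre/post study with no untrained group, and no practice trial of the test is described.

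The overlap is also uneven. It can arise in Scenario 02 and not in Scenario 01, and scenario is decided by equipment access, not by randomisation. The Option B aerobic-change variable may therefore carry a scenario difference that has nothing to do with aerobic capacity. At stake is the aerobic-capacity part of Aim 2. Under Study Plan/Options (section 3), Option B is the only route until Option A is cleared to resume, so the affected share of the sample could be material.

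**Working it through.** **No stated figure applies.** The plan gives no correlation, effect size or power for aerobic capacity. Its Aim 2 power statement (80% for a correlation of 0.34) concerns change in neuroplasticity against change in cognition. It reproduces at 80 x 0.80 = 64 evaluable participants (79.0% by Fisher z), but it says nothing about this outcome and is not used below.

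**Exposure, from the plan's own numbers.**
- A-B sequences per block: 1 + 3 = 4, so each exercise gets 4 one-minute bouts. Check: 2 exercises x 4 minutes = 8 minutes of work per block, as stated.
- Exercises per session: 5 blocks x 2 = 10, as stated. Only six are pictured, so at least four come from outside the figure.
- Sit to stand, when used, takes 4 of 5 x 8 = 40 work minutes, or 10%.
- With "24 aerobic exercise sessions", the ceiling is 4 x 24 = 96 one-minute bouts between the two tests. The floor is zero, because nothing assigns the exercise to any participant or session.

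**Test and training side by side.** They share the movement and the one-minute length. They differ in effort: the test asks for as many repetitions as possible after seated rest, while training is paced to perceived-exertion and heart-rate targets and can be modified for each participant.

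**What a scenario difference could do (assumed values only).** Let a fraction p of Option B be in Scenario 02. Let practice raise every one of their counts by d, in SD units of true aerobic change, with true aerobic change not differing by scenario. The added variance is p(1-p)d². If cognitive change does not differ by scenario either, the pooled correlation is multiplied by 1/sqrt(1 + p(1-p)d²).
- p = 0.5: d = 0.5, 1, 1.5 gives 0.0625, 0.25, 0.5625 added, and factors of 0.97, 0.89, 0.80.
- p = 0.25 or 0.75: the same d gives 0.047, 0.188, 0.422 added, and factors of 0.98, 0.92, 0.84.

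If cognitive change also differs by scenario, by e within-scenario SDs, a correlation appears with no true link: p(1-p)de / sqrt[(1 + p(1-p)d²)(1 + p(1-p)e²)]. For p = 0.5, d = 1, e = 0.5 this is 0.125 / sqrt(1.25 x 1.0625) = 0.11. With e = -0.5 it is -0.11. The sign of the bias is therefore open.

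In this model a uniform shift leaves the correlation within each scenario unchanged. That is why a scenario term and a by-scenario analysis deal with it. Variation between individuals in practice gain within Scenario 02 would remain.

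**The case against.** A reader might infer that all Scenario 02 participants train the test in its own format. The documents do not support that. The figure is a sample, other options and modifications are allowed, and training is paced to intensity targets, not to maximal repetitions. The 96 bouts are a ceiling.

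A reader might also infer that Aim 2 will mistake practice for aerobic gain, or that a true correlation of 0.34 would shrink by a known amount. The first asserts a result; the text supports only that the two cannot be told apart. The second borrows a figure stated for plasticity against cognition and needs a practice variance that appears nowhere in the plan.

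Option A has movement overlap too: participants walk or trot in training and are tested by a shuttle walk. This stands as a general limit of field tests. The difference is that Option A describes one training mode for everyone, so overlap there does not divide participants by equipment access.

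The heart rate recorded around the sit-to-stand test might seem a ready second index. It is not a clean one, since it depends on how many repetitions were done and uses the same movement.

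Finally, Aim 1 and the stated Aim 2 hypothesis (plasticity with cognition) do not use the count, and the multivariable model names only TMS plasticity, which Option B does not have. Option B aerobic capacity enters Aim 2 through the Objectives and section 8. This limits the reach of the point but does not remove it.

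**Conclusion.** The point holds as a limit on interpretation with a cheap remedy. For Option B participants without equipment who are given sit to stand, a change in the count cannot be read as aerobic change alone. Because scenario follows equipment access and is absent from the model, a between-scenario difference of non-aerobic origin could enter the Aim 2 aerobic-capacity analysis.

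The size is not known. Exposure lies between 0 and 96 one-minute bouts per participant; the number of participants affected and the practice gain are not in the documents. The direction is not fixed either: practice unrelated to cognition weakens an association, while a scenario difference in cognitive change could create one of either sign. The multipliers above rest wholly on assumed p, d and e, and are not estimates for this trial. There is no contradiction in the text, only an overlap that the analysis does not handle.

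**What to change.** In section 8 (Aerobic Capacity, Option B) and section 11 (Data Analysis):
- Record each Option B participant's exercise scenario, and whether and in how many sessions sit to stand was trained.
- Include scenario in the Option B analysis of aerobic-capacity change against plasticity and cognitive change.
- Repeat that analysis by scenario, with Scenario 01 alone as a sensitivity analysis.
- In participants who trained the movement, describe the change in count as sit-to-stand performance, not as aerobic capacity alone.

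The sponsor may instead choose to avoid the overlap between the tested and trained movement; how to do so is the sponsor's decision.

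Cost: a few lines of text, one record of training content, one more model term, and a weaker label for the count. No new test is needed. The Scenario 01 subset will be small and of unknown size, so it supports a consistency check more than a separate conclusion. The scenario term removes the mean difference between scenarios but not individual variation in practice gain within Scenario 02. Avoiding the overlap would cost more, since it would touch the intervention text or require a different measure.

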Principal investigator: [name]

Protocol Title: Assessing Cognitive Improvements, Brain Neuroplasticity and the Role of Genetic Factors After Aerobic Exercise in Sedentary Adults

IRB Number: 20180926

NCT: NCT03804528

Document Version Date: 2/22/2021

IRB Study Number: 20180926

1) Protocol Title

Assessing Cognitive Improvements, Brain Neuroplasticity and the Role of Genetic Factors After Aerobic Exercise in Sedentary Adults

2) Objectives

The overall goal of the proposed study is to evaluate the effects of an 8-week aerobic exercise program on cognition and determine the relationship between cognitive improvements and neuroplasticity. Limited to Option A (See Study Options section), we will also explore the effect modification of BDNF levels and BDNF allelic status, and APOE4 status on cognitive response after exercise.

Aim 1: Quantify improvements in cognitive performance after 8 weeks (150 min per week) of moderate intensity aerobic exercise in sedentary adults ≥ 55 years of age. **H1:** We hypothesize that we will see improvements in overall cognitive performance after exercise, and greater improvements in some of the cognitive domains (e.g., in executive function and processing speed, as opposed to memory or language).

Aim 2: Determine an association between changes in plasticity, aerobic capacity, and cognitive performance overall and by cognitive domain, after 8 weeks of moderate intensity aerobic exercise in sedentary adults ≥ 55 years of age. **H2:** We hypothesize that a greater response in the brain plasticity will be associated with greater improvements in cognitive performance overall and in executive function after exercise.

Aim 3 (Option A): Explore the effect modification of BDNF (levels and Val66Met) and APOE e4 on cognitive response after exercise. **H3:** We hypothesize that individuals with greater levels of BDNF, being Val carriers or APOE e4 carriers will have greater improvement in cognitive performance after exercise.

3) Study Plan/Options

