- Exercise Questionnaires (literacy, self-efficacy, barriers/motivators)

Visits #4-15: Physical exercise Intervention-Moderate Intensity (estimated time per visit: 60 minutes 3 times per week for weeks 2-5, total of 4 weeks of Moderate Intensity Exercise)

- Assessment of vitals (blood pressure, heart rate)
- 60 minutes of aerobic exercise (includes 5 minute warm-up/5 minute cool-down)
- Re-assessment of vitals

Visits #16-27: Physical exercise Intervention-High Intensity (estimated time per visit: 60 minutes for weeks 6-9, total of 4 weeks of High Intensity Exercise)

- Assessment of vitals (blood pressure, heart rate)
- 60 minutes of aerobic exercise (includes 5 minute warm-up/5 minute cool-down)
- Re-assessment of vitals

Visit #28 Posttest assessment- Part 1 (estimated time: 3 hours, maybe completed on same day as Part 2, completed in week 10)

- Blood draw
- Gait and postural control assessment
- Review of the adverse effects
- TMS plasticity

IRB Study Number: 20180926

- Review adverse effects post TMS

Visit #29 Posttest assessment- Part 2 (estimated time: 1.5 hours, may be completed on same day as Part 1, completed in week 10)

- Cognitive test battery
- Exercise Testing
- Exercise Questionnaires (literacy, self-efficacy, barriers/motivators)

Optional Test visits:

- An additional testing combining TMS and EEG during pre and post testing will be offered to participants. This testing is performed to gather information about direct measure of neuronal activity. This would add approximately two hours to each visit.

Visit #4: TMS/EEG pretesting measure (estimated time: 2 hours)

- Review of adverse events
- Single pulse TMS plasticity measures
- EEG recording
- Review adverse effects post TMS

Visit #31: TMS/EEG post testing measure (estimated time: 2 hours)

- Review of adverse events
- Single pulse TMS plasticity measures
- EEG recording
- Review adverse effects post TMS

OPTION B: This option is an adaptation of the current methods that includes updating testing timeline to include a familiarization session. We updated our assessment to include outcome measures that are appropriate for remote delivery. We eliminated our genetic testing as it not possible to be performed remotely. In this option, in-person visits will be replaced with remote sessions.

Adaptations of the current timeline include:

Session #1a: Screening process:

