Participants will be fitted with a heart rate monitor and will be instructed to walk (or trot) to maintain 55-64% of maximal heart rate (determined by exercise test) for the first 4-weeks of exercise or to maintain 65-90% of maximal heart rate (determined by exercise test) for the second 4-weeks of exercise during each session. Participants will be supervised at all times during the exercise sessions, and will be given the opportunity to rest if they indicate that they are uncomfortable. During all exercise sessions a research personnel who is trained in Basic Life Support or Cardiopulmonary Resuscitation (CPR) and First Aid certified will be present on site. During this session, heart rate and participant's exerted effort (measured with the Borg scale⁴⁰) will be monitored prior to the session, every 10 minutes of the 50 minute session and 5 minutes after the end of the session. The Borg scale is a numerical scale where 6 represents rest (no effort), and 20 represents maximal effort (see photo on the right).

A PT will be available by phone if subjects are reporting excessive discomfort in need of evaluation, and an appropriate referral will be made as necessary. In the event of an absence, participants will have the opportunity to make up the missed session.

20 Point Borg Scale			
RPE Rate of Perceived Exertion			
POINT	EFFORT	DESCRIPTION	% OF MAXIMUM HEART RATE
6	No Exertion	Little to no movement, very relaxed	20%
7	Extremely Light	Able to maintain pace	30%
8			40%
9	Very Light	Comfortable and breathing harder	50%
10			55%
11	Light	Minimal sweating, can talk easily	60%
12			65%
13	Somewhat Hard	Slight breathlessness, can talk	70%
14		Increased sweating, still able to hold conversation but with difficulty	75%
15	Hard	Sweating, able to push and still maintain proper form	80%
16			85%
17	Very Hard	Can keep a fast pace for a short time period	90%
18			95%
19	Extremely Hard	Difficulty breathing, near muscle exhaustion	100%
20	Maximally Hard	STOP exercising, total exhaustion	

Source: [name], M.D.

Exercise Questionnaires:

We will perform the Lifetime Physical Activity Questionnaire, Exercise Self-Efficacy, and Barriers and Motivators to Exercise questionnaires.

[figure not shown]
OPTION B METHODS

Study Kit

Participants will receive a study kit including items that have been previously sanitized using alcohol-based solution greater than 70% will be shipped to the participant's home. The study kit will include:

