
Individuals who have access to exercise equipment at home (treadmill, stationary bike, elliptical)
 
 
  
Walking and running on treadmill
 
 
  
Elliptical
 
 
 
 
  
Stationary bike
 
 
  
Stationary recumbent bike
 
 
	
Individuals who do not have equipment at home will be given a sequence of free weight and machine exercise, for example with marching in place, and body weight exercise.
 
 
  
Marching in place
 
 
  
Squat
 
 
  
Whole body
 
 
 
 
  
Sit to stand
 
 
  
Wall push-ups
 
 
  
Jumping jacks
 
 

<small>*Other exercise options and modifications for each exercise will be made available based on participant's ability and safety.</small>	

Exercise parameters for both scenarios: Moderate to vigorous (5 minutes warm-up, 40 minutes of continuous exercise in the target zone, and a 5-minute cool-down); RPE 11-13 (somewhat hard) weeks 1-4, and 13-15 (hard) weeks 5-8; Target Heart Rate 54-65% weeks 1-4, 65-89% weeks 5-8

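### Aim 1 states 150 minutes of exercise per week, but Option B schedules 120, in 8-minute bouts that the exercise-parameters line wrongly calls continuous

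*Combined protocol and SAP*

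**What the plan says.** Section 2 (Objectives) gives one dose for the whole study: "Quantify improvements in cognitive performance after 8 weeks (150 min per week) of moderate intensity aerobic exercise".

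For Option A, section 7 (Study Timelines) describes each exercise visit as "60 minutes of aerobic exercise (includes 5 minute warm-up/5 minute cool-down". Section 9 (Physical exercise Intervention, Option A) has sessions three times a week for 8 weeks, 24 in all. It records heart rate and effort "every 10 minutes of the 50 minute session". Rest is offered if a participant is uncomfortable; none is scheduled.

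For Option B, section 9 (Adaptation of Our Physical exercise Intervention) keeps three sessions a week for two months. The parameters line, which covers people with and without home equipment, reads "Moderate to vigorous (5 minutes warm-up, 40 minutes of continuous exercise in the target zone, and a 5-minute cool-down". The text that follows says "Mandatory rest and water breaks will be incorporated into the exercise session every 8 minutes for two minutes each", totalling 10 minutes of rest, and lists this separately from 40 minutes of exercise whatever the mode. The session is then laid out as "five, 10-minute timed blocks consisting of eight minutes of exercise and two minutes of rest", with a timetable giving the same work and rest minutes to both groups.

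The Data Analysis part of section 11 tests Aim 1 with a paired t-test of cognition before and after exercise. The adjusted model lists age, sex, race-ethnicity and education, but not option. No separate weekly target for Option B appears.

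**The concern.** Two statements about the intervention do not match the schedule. The weekly minutes in Aim 1 fit Option A but not Option B, and the parameters line describes unbroken exercise where the timetable has bouts of at most 8 minutes.

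Aim 1 asks how much cognition changes after a stated dose. If both options are pooled and the report repeats the 150 minutes, the estimate is attached to a dose that part of the sample was never prescribed. Section 4 (Background) names exercise dose among the things that need better understanding, and says that data gained by adding Option B are meant to support a later NIH submission. A misdescribed dose could be carried into that design.

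**Working it through.** **Inputs.**
- Aim 1: 150 minutes per week (section 2).
- Option A session: 60 minutes, including 5 of warm-up and 5 of cool-down (section 7); 50-minute session (section 9).
- Option B session: five blocks of 8 minutes' work and 2 minutes' rest, plus 5 of warm-up and 5 of cool-down (section 9).
- Frequency: 3 per week in both options; 24 exercise sessions (section 9, Study Design).

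**Step 1: reproduce the plan's figure.** Option A exercise minutes are 60 − 5 − 5 = 50 per session, and 50 × 3 = 150 per week. This equals Aim 1 exactly, so the 150 is read as excluding warm-up and cool-down.

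**Step 2: apply the same rule to Option B.** Work minutes are 5 × 8 = 40 per session, and 40 × 3 = 120 per week. The shortfall is 150 − 120 = 30 minutes per week, and 30 / 150 = 20%. Over 24 sessions: 40 × 24 = 960 against 50 × 24 = 1,200, or 240 minutes fewer.

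**Step 3: try other ways of counting.**

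| Minutes counted | Option A, per week | Option B, per week |
|---|---|---|
| Work only | 50 × 3 = 150 | 40 × 3 = 120 |
| Work, warm-up and cool-down | 60 × 3 = 180 | 50 × 3 = 150 |
| Work and scheduled rest | 50 × 3 = 150 (none scheduled) | 50 × 3 = 150 |
| Whole session | 60 × 3 = 180 | 60 × 3 = 180 |

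Only the third row gives 150 in both options, and it does so by counting rest as exercise. The Option B text lists the 10 minutes of rest apart from the 40 minutes of exercise, so that row is not the protocol's own count.

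**Step 4: check the word *continuous*.** The parameters line adds up to 5 + 40 + 5 = 50 minutes. The timetable runs 5 + 5 × 10 + 5 = 60. The 10-minute difference is the mandatory rest that the line omits. The longest scheduled unbroken work is 8 minutes.

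**The case against.** Within Option B the protocol is largely consistent. The parameters line, the text and the timetable all arrive at 40 minutes of work; only the word *continuous* and the omitted rest are out of step. The introduction to Option B also says openly that the intervention was modified. The remark that equipment users exercise as in Option A can be read as being about the use of the machines, since the same paragraph then sets 40 minutes for every mode. No aim or analysis tests dose. All of this stands. It confines the point to the stated weekly dose and the description of the bouts.

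A reader might go further in three ways that the documents do not support.

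- *Staff could not tell whether a session complied.* The timetable is set out minute by minute, the breaks are called mandatory, and the text presents that format as the standard to follow. The timetable is the operative schedule.
- *Time in the heart-rate zone falls short by more than 20%, because heart rate must climb again after each rest.* It could equally stay in the zone through a 2-minute rest, and Option A participants may also stop when uncomfortable. The protocol gives no basis for a figure, and Option A heart rate is specified only every 10 minutes during exercise, so comparable minutes in zone are not assured.
- *The intensity targets are unworkable.* The line gives "Target Heart Rate 54-65% weeks 1-4, 65-89% weeks 5-8" with no stated base, and of the sit-to-stand test section 8 says "The test is submaximal and will be used to dose the aerobic exercise intensity". The missing base is a gap in description. But on the protocol's Borg table the effort target for weeks 1–4 (11–13, or 60–70%) overlaps the heart-rate target at 60–65%, so both can be met. Changing either target would alter the prescription, which this point does not call for.

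**Conclusion.** The point holds as a misstatement of the prescribed dose. Option B schedules 120 minutes per week against the 150 in Aim 1, 20% less, in bouts of at most 8 minutes.

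This rests on one inference, that the 150 excludes warm-up, cool-down and rest. The exact match with Option A supports the first two exclusions, and the separate listing of rest in Option B supports the third. The figures are scheduled work time, not delivered time or time in zone.

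The mandatory breaks are not at fault, and nothing here changes the stated sample size or power. Nor would a difference between options measure the effect of dose: participants may choose Option B by preference, and the cognitive battery and exercise setting also differ.

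**What to change.** Keep the breaks and correct the description.

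1. Section 9, Option B exercise parameters: replace the 40 continuous minutes with *five 8-minute bouts in the target zone, each followed by 2 minutes of rest (40 minutes of work)*.
2. Section 2, Aim 1: state *150 min per week (Option A) or 120 min per week (Option B)*.
3. Section 9, Option B text: make clear that people using home equipment follow the block format too.
4. Section 11, Data Analysis: report the Aim 1 change by option beside the pooled result, as description and not as a test of dose.

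The cost is a wording amendment and one added table, with no new data. The result can no longer be presented as the effect of a single dose, and each by-option estimate will be less precise than the pooled one.
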